1.1 Study hypothesis

The hypothesis of the study is that in IOM of long bone fracture, a short antibiotic treatment is equally effective as a long antibiotic treatment in patients selected for debridement and implant retention. Antibiotic duration can be selected according to the time of diagnosis of IOM as it takes into account the biofilm formation and the state of fracture consolidation:

- a) In patients with early infections (those that occur in the first 2 weeks after implantation of the osteosynthesis material) in whom early debridement is performed, it is possible to shorten the duration of antibiotic treatment to 8 weeks (versus 12 weeks);
- b) In patients with delayed infections (those that occur between 3 and 10 weeks after implantation of the osteosynthesis material) in whom it is not possible to remove the implant due to instability/lack of fracture healing, it is possible, after surgical debridement, to shorten the duration of antibiotic treatment to 12 weeks (vs. maintaining antibiotic treatment until fracture healing or implant removal).
- c) In patients with late infections (those that occur more than 10 weeks after implantation of the osteosynthesis material) healing is not possible until the implant is removed, but when removal is not possible, antibiotic therapy can be maintained until fracture healing or implant removal.

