1.4 Primary endpoint

The primary endpoint is the variable "cure" composed by all of the following: a) clinical cure in the test of cure (TOC) (see definition below); b) radiological healing; c) definitive soft tissue coverage at TOC.

The definitions for all the outcomes are specified in the study protocol. The TOC will be performed 12 months after the end of antibiotic therapy prescribed to treat IOM following DAIR, except in patients with delayed infections randomized to the long-treatment regimen (until fracture union) who receive 6 months or more of antibiotic treatment, which will be evaluated 18 months after the start of the study (or randomization).

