5. STATISTICAL ANALYSIS

5.1 Primary endpoint

The primary endpoint will be collected as a dichotomous variable (yes/no). The primary analysis will be the absolute difference in the proportion of patients reaching the composited primary outcome variable “cure” in the study arms (with one-sided 95% confidence interval) in the ITT population, with the long antibiotic treatment as the reference group. The specific reasons for not reaching overall success (failure, withdrawals, death, etc.) will be specified in both study arms.

A secondary analyses will include subgroups analysis for the primary outcome using the same procedure, and the comparison of the composite variable components (clinical cure, radiological healing and soft tissue coverage) in the PP and CEP, after excluding incorrectly assigned patients.

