5.5 DOOR/RADAR analysis

In order to provide additional information of the different components of the primary endpoint, an analysis with desirability of outcome ranking (DOOR) and response adjusted for duration of antibiotic risk (RADAR) will be performed. First, patients will be classified according to the following ordinal system:

Category	Failure	No bone healing	No soft tissue coverage	Severe adverse event
1	No	No	No	No
2	No	No	No	Yes
3	No	No	Yes	Yes or no
4	No	yes	Yes or no	Yes or no
5	Yes	Yes or no	Yes or no	Yes or no

Second, in case of tie, the duration of total antibiotic duration will be considered; patients with a shorter duration will be given a better category. Finally, the probability of having a worse ranking among patients treated with a short antibiotic regimen than among patient with a long antibiotic regimen will be calculated; the upper bound of the 95% CI of the probability should be $>50\%$ to suggest non-inferiority of short antibiotic regimen.

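### The DOOR/RADAR decision rule is reversed: a short arm that ranks equal or worse always meets it, and one that clearly ranks better fails it

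*SAP*

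**What the plan says.** SAP section 5.5 adds a DOOR/RADAR analysis with a supporting purpose: "In order to provide additional information of the different components of the primary endpoint". Patients are placed in five ordered categories. Category 1 is the best (no failure, bone healed, soft tissue covered, no severe adverse event) and category 5 is failure. Then "in case of tie, the duration of total antibiotic duration will be considered", and the shorter duration gets the better place. The quantity estimated is "the probability of having a worse ranking among patients treated with a short antibiotic regimen than among patient with a long antibiotic regimen". The decision rule is that "the upper bound of the 95% CI of the probability should be $>50\%$ to suggest non-inferiority of short antibiotic regimen".

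No other section restates or corrects this rule. Section 5.1 defines the primary analysis separately, as an absolute difference in cure in the ITT population, "with one-sided 95% confidence interval". Section 5.5 does not say whether its own 95% interval is one- or two-sided.

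**The concern.** The estimated probability is unfavourable to the short arm when it is high, yet the rule rewards a high upper bound. Applied literally, it cannot exclude a worse-ranked short arm and it is met more often the worse that arm does. The result that should support the short regimen, an interval wholly below 50%, would be reported as not suggesting non-inferiority. This is the only decision criterion in section 5.5, and a change of direction made after the data are seen would look driven by the results.

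**Working it through.** **Logic (no assumptions).** Let θ be the probability that a short-arm patient ranks worse than a long-arm patient. θ = 50% means no difference in ranking and θ > 50% means the short arm ranks worse. The upper bound U is never below the estimate.

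- Estimate of 50% or more: U exceeds 50%, so the rule is met at any sample size.
- Whole interval below 50%: U is below 50%, so the rule fails.
- For an estimate below 50%, a wider interval raises U and helps to meet the rule.

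**Could another word be the slip?**

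| Reading | What meeting the rule shows |
|---|---|
| As written: upper bound of P(worse) > 50% | short arm not significantly better |
| *worse* read as *better* | short arm not significantly worse; imprecision still helps |
| *upper* read as *lower* | short arm significantly worse |
| *>* read as *<* | short arm significantly better ranked |

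Of these single changes, only turning the inequality gives a rule that supports the short regimen.

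**Hand check of size.** The SAP gives no number per arm, so 75 and 150 are assumed. Without ties, near θ = 0.5, SE = √[(2n+1)/(12n²)].

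- n = 75: √(151/67,500) = 0.047; 0.5 − 1.96 × SE = 0.407.
- n = 150: √(301/270,000) = 0.033; 0.5 − 1.96 × SE = 0.435.

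Estimates above about 41% or 43.5% therefore meet the rule, and better ones fail.

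**Simulation (2,000 trials per scenario).** Assumed inputs:

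- 75 or 150 per arm.
- Long-arm cure 80%, except in the 95% v 70% scenario.
- Severe adverse events in 10% or 20% of cures.
- Non-cures split 10/40/50% over categories 3, 4 and 5.

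θ is a Mann–Whitney-type probability with a placement-value standard error and a two-sided 95% interval.

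For the tie-break, short-arm durations are 56 days (early) and 84 days (delayed), and early-long is 84 days, from the 8 and 12 weeks in section 1.1. The delayed-long duration is not fixed: section 1.1 runs it to healing or implant removal, and section 1.4 speaks of those "who receive 6 months or more of antibiotic treatment". It was set at 180 days or spread evenly over 42–270 days, with 30–70% early infections. Remaining equal durations count one half.

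Share of trials meeting the rule as written:

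| Short-arm v long-arm cure | Planned duration tie-break | Five categories only, ties one half |
|---|---|---|
| 60% v 80% | 49–96% | 100% |
| 70% v 80% | 1–69% | – |
| 80% v 80% | 0–18% | 97–98% |
| 90% v 80% | 0–1% | 45–77% |
| 95% v 70% | – | 0.1–11% |

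In all 28 combinations of size, severe-adverse-event rate, tie handling and early share, the frequency never rose as short-arm cure went from 60% to 90% against 80%. Imprecision helps: on five categories at 90% v 80% with 10% severe adverse events, the rule is met in about 70% of trials at 75 per arm and about 46% at 150.

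With a one-sided interval the pattern is the same. The tie-break column becomes 36–94%, 1–59%, 0–12% and 0–0.2%. The five-category column becomes 100%, about 95%, 33–64% and 0–5%.

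**Second set of assumptions.** Here all category ties go to the short arm, with 50 to 200 per arm and 1,500 trials per scenario. The long arm is 70/8/5/7/10% over categories 1–5.

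| Short arm, categories 1–5 (%) | Mean θ | Rule met |
|---|---|---|
| 5/5/10/20/60 | 0.82 | 100% |
| 35/10/10/15/30 | 0.54 | 99.3–100% |
| 70/8/5/7/10 (equal) | 0.24 | 0–1.1% |
| 88/4/2/2/4 | 0.10 | 0% |

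No simulated trial with an estimate above 50% failed the rule.

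**The case against.** The strongest reply concerns weight and framing.

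- **The analysis is supplementary.** No sample size, interim decision or population depends on it, and the probability with its interval can be read without the rule. This stands: the harm is a wrong verdict attached to a correct estimate.
- **The starkest percentages are not from the planned analysis.** The 97–98% for equal arms comes from splitting ties; with the duration tie-break it is 0–18%. In the main tie-break simulation the mean θ stays below 50% (about 0.43–0.49) even when short-arm cure is 20 points worse. This stands too. *Worse* here means worse on the ranking, and *always* is exact for an observed estimate. For a true θ above 50%, chance exceptions were at most 0.7% in the scenarios run.
- **The turned rule is not a test of clinical efficacy.** It is essentially the complement of the present one. With the tie-break it would be met in 4–51% of trials when short-arm cure is 20 points worse (100 minus 49–96) and 31–99% when 10 points worse (100 minus 1–69). This is correct, and it is why the claim must be limited to ranking. Strict non-inferiority would need a threshold above 50%, which the SAP does not give.
- **The symbol may be a slip of typing.** Possibly, but the text as it stands is unambiguous and would be applied as written.

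None of this makes the present inequality usable.

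**Conclusion.** The rule is wrong as written. That any estimate of 50% or more meets it, and that an interval wholly below 50% fails it, follows from the definitions alone. The frequencies rest on assumed sample sizes, cure and adverse-event rates, category splits and durations; the direction does not change across them. With identical outcomes and the planned tie-break, the short regimen would fail the rule in 82–100% of simulated trials (100 minus 0–18). The effect is confined to section 5.5, but there it reverses the conclusion, so it should be corrected before the data are analysed.

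**What to change.** Replace the final clause of section 5.5 with wording such as: *with ties that remain after the duration comparison counted as one half, a better DOOR/RADAR ranking of the short regimen is suggested if the upper bound of the 95% CI of the probability of a worse ranking is <50%*. With that tie convention, this is the same as a lower bound above 50% for the probability of a better ranking. State whether the interval is one- or two-sided.

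Describe the result as one on the ranking, not as evidence of non-inferior clinical efficacy, since the tie-break uses a duration that randomisation largely, though not always, makes shorter in the short arm. If the sponsor wants a non-inferiority claim here, it must state and justify a threshold above 50% in advance.

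Optionally, also report the five-category probability before the duration tie-break, with ties counted as one half.

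Cost: one clause, plus one extra output line from the same data if the option is taken. The primary and secondary analyses do not change.
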